6.2 Study Agents/Interventions

A description of the SHUTi program is outlined in the background and methods (under "intervention").

7 Reporting Procedures

Patients participating in this study may experience side effects, toxicities, and adverse events associated with completion of study procedures. Adverse events reported under this protocol will be limited to those events which are possibly, probably or definitely related to the research described in this protocol. The clinical care team overseeing the primary screening protocol will report any adverse events that are related to the screening protocol (14-AA-0181). An adverse event is defined as any untoward medical occurrences that 1) result in death, 2) are life-threatening, 3) require hospitalization, 4) cause persistent or significant disability / incapacity, 5) result in congenital anomalies or birth defects, 6) are other conditions which in the judgment of the investigators represent significant hazards. All events will be reported to the IRB in accordance with NIH Human Research Protection Program Policy #801 (Reporting Research Events). The PI will provide continuous, close monitoring of data and side effects, toxicities, and adverse events to identify trends. The PI will be responsible for revising the protocol as needed to maintain safety. All adverse events will be reported in aggregate at the time of continuing review, unless otherwise granted waiver by the IRB. If it is determined from the review of the aggregate data that an event is occurring at a greater frequency or level of severity than previously expected, it constitutes an unanticipated problem (UP) and will be reported in accordance with the reporting requirements outlined in the NIH Human Research Protection Program Policy #801.

Protocol Number: 18-CC-0079

8 Data Safety and Monitoring Plan

Clinical monitoring will be conducted in accordance with the Clinical Center (CC) Monitoring Policy. In brief, protocols will be submitted to the CC Quality Assurance Coordinator who will determine the frequency and complexity of monitoring based on the IRB assigned risk and patient populations. Monitoring will be performed by the CC Quality Assurance Coordinator.

Participants will be discontinued/withdrawn from the study if any of the following events occur: participant requests to be removed from study, participant is admitted to an addiction inpatient treatment program at the NIH or elsewhere within 9 weeks of discharge from 1SE (upon PI discretion), participant exhibits any condition which the MAI finds CBT-I to be a hazard to the participant (i.e. participant seems agitated, onset of increasing paranoia) participant is unable to comply with study-related procedures (i.e. SHUTi program recommendations and/or "homework), and/or participant develops a medical illness or condition that requires a new hospital admission.

10 Data/Records Management

The PI will be responsible for assuring that all investigators follow the plan for protecting the confidentiality of information and data provided by research participants. Assessments collected via paper-and-pencil questionnaires will be de-identified through the use of non-identifiable codes. The key to the code will be kept securely and separate from data and samples. Participant information will be

Protocol Number: 18-CC-0079

maintained in secured databases and computers in locked files and a locked office. Paper records will be maintained in locked files and a locked office. Access to samples and data will be limited to authorized study personnel. The PI will be responsible for overseeing entry of the data (quantitative and interview transcripts) into a password protected electronic system and ensuring data accuracy, consistency, and timeliness.

Information to be collected via the internet-based insomnia treatment program, SHUTi, will include participants' responses to individual questions within the program and the dates and times questions are modules were completed. Personnel at the University of Virginia (where the servers are located) will periodically download this data, which contains no PII and is identified only by user ID and forwarded to research personnel. Participants will not be asked to provide any PII in the course of their engagement in the SHUTi intervention and/or education-only programs. At the initial meeting for consenting and baseline assessment, participants will be provided with a unique user login ID and a temporary password. The participant will be required to change the password at initial logon to the website to a personal one that he or she will recall. Only the participant and the study staff will have the authority to access the participant's responses to the components of the intervention. All baseline and follow-up assessments not part of the SHUTi program will be completed in person or over the phone with paper-and-pencil questionnaires and will be administered by a member of the research team.

The SHUTi program has the ability to send automated pre-developed introductory, reminder, congratulatory, and (insomnia) relapse prevention emails to participants, which serve to enhance engagement and clinical outcomes. The content of each email is included in the appendices. The e-mails are automatically sent by the program and not manually by an individual. The e-mail content explicitly states that participants should not respond to the e-mail. No PII or protected health information is sent in the e-mails. In this project, all participant interaction with the program will be de-identified. Several other projects that have tested the SHUTi program have used an "e-mail exchange" to separate participant's real email address from the SHUTi program. An e-mail exchange is a set of dummy email address set up through a common e-mail provider such as "g-mail." The SHUTi program will e-mail a dummy email address. The dummy address will then forward the e-mail to the participants' real e-mail address. Only study personnel will have access to the document linking the dummy e-mail with the participants' e-mail, which will be accessible only to authorized study personnel as with other PII. Participants will be informed of this process during informed consent procedures. Data will be stored in locked cabinets and a password-protected database, in accordance with NIH records management policies, until it is no longer of scientific value.

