2.2 Phase II

Randomization will be achieved using a random number generator, assigning equal numbers of participants to each of the two conditions. The PI and AIs will remain blind to the randomization scheme until each study participant is deemed eligible and signs the consent form.

Intervention/control groups (Phase II only)**:

1. **Intervention group:** 6 sessions (“modules”) of SHUTi intervention (at least one module completed while inpatient, the rest while outpatient): In SHUTi, customization is based on multiple variables, including sleep diary responses. The SHUTi program tailors specific recommendations based on sleep diary responses or other input within the program (e.g., responses on the Dysfunctional Beliefs and Attitude Scale trigger recommendations for specific cognitive restructuring strategies).
2. **Control group:** education/monitor only (insomnia education web-based program that participants access and read at their own pace – contains no customization of program based on sleep diary responses). Participants in the control group are given educational information (like they might see on WebMD or National Sleep Foundation websites), but are left to apply it themselves.

**Participants who are randomly assigned to the intervention condition will be granted access to the program free of charge for up to six months from the start of the program. Participants who are randomly assigned to the education-only condition will be given access to the full SHUTi program three months after discharge upon request. Similarly, participants who are randomly assigned to the intervention condition will be granted access to the education materials provided to the education-only condition participants three months after discharge upon request.

All participants enrolled in this study will first be admitted under the screening and assessment protocol on the 1SE clinic (14-AA-0181), which includes adults at least 18 years of age seeking treatment for alcohol use disorders. Once consented and enrolled into the inpatient treatment, screening, and research protocol, participants are screened and recruited enrollment in additional studies for which they meet eligibility criteria (including the study described herein). Study participants will be asked to

Protocol Number: 18-CC-0079

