come back to the Clinical Center post-discharge for a follow-up visit to complete a face-to-face semi-structured interview (Phase I participants only) and questionnaires (Phases I and II participants). If participants are unable to return for the follow-up visit, we will attempt to conduct the surveys and interview via phone.

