2.4 Study Measures

Feasibility and acceptability measures. Participants enrolled during Phase I will be asked to start the SHUTi modules prior to being discharged from inpatient treatment. They will be invited to participate in a short interview after they complete the first SHUTi module in order to gather additional information on program delivery and acceptability in the population. We will also utilize the Internet Evaluation and Utility Questionnaire (Ritterband et al., 2008) at the pre-discharge interview, which is a 16-item measure

Protocol Number: 18-CC-0079

designed to assess usability, likeability, usefulness, understandability, and convenience of the intervention. We will also implement an exit assessment for Phase I *and* II participants. At the exit assessment, we will use the Internet Impact and Effectiveness Questionnaire, the Internet Evaluation and Utility Questionnaire, and the Internet Intervention Adherence Questionnaire (Ritterband et al., 2008). The Intervention Impact and Effectiveness Questionnaire is a 14-item measure designed to assess perceptions of the impact of the program. Responses on all questionnaires related to utility and impact are rated on 5-point Likert scales from 0 (“not at all”) to 4 (“very”). Participants will complete these assessments with a member of the research team who will take notes on participants’ comments for each question. Open-ended questions (used in Phase I only) will be audio recorded and the entire session (including the questionnaires) are expected to last between 20-60 minutes, depending on the participant's responses. Additional measures of program adherence (in the experimental group, for both Phases I and II) will be measured by three variables: login count (goal of two per week), completed diary count (minimum of five per week), and number of “cores” completed out of a possible six cores.

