Insomnia Severity Index (ISI). The ISI is a seven-item global index of self-reported insomnia symptom severity. It is valid, reliable, sensitive to changes in insomnia treatment (Bastien, Vallieres, & Morin, 2001; Morin, Belleville, Belanger, & Ivers, 2011) and validated for online use (Thorndike et al., 2011). Seyffert and colleagues (2016) categorized insomnia severity by scores as follows: 0-7 = no clinically significant insomnia, 8-14 = subthreshold insomnia, 15-21 = moderate insomnia, and 22-28 = severe insomnia. Changes in the ISI over time will be a primary outcome measure. The ISI is collected within the SHUTi intervention program at the beginning of each core, but participants in both Phase I and Phase II will also complete a paper version of the ISI during the pre-, mid-point, and post-test assessments.

Daily sleep and symptom diaries. Prospectively collected sleep diaries are a proven method for assessing insomnia and track treatment effects (Carney, et al., 2012; Buysse, Ancoli-Israel, Edinger, Lichstein, & Morin, 2006) and have been used for other sleep studies among patients on 1SE (inpatient and outpatient). Participants will be asked to complete at least five out of every seven days of daily sleep and symptom diaries. These diaries will include sleep/wake times, time in bed, sleep onset latency, number and duration of awakenings, sleep quality, naps, alcohol consumption, any over-the-counter or prescription medications used to help with sleep (participants will be instructed to include any marijuana use in this section), and open-ended comments. For the experimental group, diaries will be used to assess adherence to their “sleep window,” based on actual time in bed as a proportion of prescribed time in bed. We will cross-validate diary-reported sleep duration with actigraphy data when possible. Secondary outcome measures captured in the diaries will include a categorical measure of relapse (i.e. whether the participant reports any drinking post-discharge) as well as quantity and frequency of drinking, which will be calculated in the case of relapse, as well as all other diary variables.

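### Section 9 withdraws participants from the study, not only the programme, for inability to comply or for addiction readmission, and nothing continues their outcome assessment, so outcome loss may be informative in either direction

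*Combined protocol and SAP*

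**What the plan says.** Section 9 (Clinical Monitoring Plan) opens its list of withdrawal reasons with "Participants will be discontinued/withdrawn from the study if any of the following events occur". The object is the study as a whole. Two of the reasons matter here.

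- **Compliance:** "participant is unable to comply with study-related procedures (i.e. SHUTi program recommendations", with homework as the other example. No threshold is set.
- **Readmission:** "participant is admitted to an addiction inpatient treatment program at the NIH or elsewhere within 9 weeks of discharge" from the unit, subject to the PI's discretion. On blinding, Section 2.2 says only that "The PI and AIs will remain blind to the randomization scheme until each study participant is deemed eligible and signs the consent form".

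The nearest provision for later data is in Section 2.2: "If participants are unable to return for the follow-up visit, we will attempt to conduct the surveys and interview via phone". It concerns people who cannot travel and does not mention people who have been withdrawn.

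Controls receive self-paced reading and "are left to apply it themselves". Section 2.4 treats adherence as something to record: "Additional measures of program adherence (in the experimental group, for both Phases I and II) will be measured by three variables" (logins, diaries and cores).

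Section 3 fits a mixed model with group, time and their interaction to the ISI. It uses whatever data were collected and claims unbiasedness under MCAR or MAR. The number of cores completed enters only a separate dose analysis within the treatment arm.

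**The concern.** Followed as written, Section 9 ends data collection for people selected by how they are doing. The only compliance examples are SHUTi tasks, and Section 1 describes SHUTi as demanding five diaries in seven days before the next core opens. No comparable demand is described for the education programme, so the compliance reason may remove more people from the SHUTi arm. The readmission reason is closely tied to drinking, a secondary outcome, and is applied by someone whose blinding is not described after consent.

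Outcomes that were never collected cannot be recovered at analysis. The mixed model keeps data from before withdrawal. It corrects for the loss only as far as those data predict what was lost, and neither adherence nor drinking is in the primary model. At stake are the comparisons on ISI and actigraphy sleep efficiency, and the relapse assessment at 6-7 months. For the last of these, the documents do not allow a direction of bias to be stated.

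**Working it through.** **Inputs from Section 3:** 60 participants allocated 1:1, attrition 40%, correlation 0.6, two-sided alpha 0.05, power 0.80, detectable effect 0.84. **Assumptions, not in the documents:** the share withdrawn, the benefit they keep, and any prognostic gap.

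**1. The plan's own figure.** Completers: 60 × 0.6 = 36, or 18 per arm. SD of change = √(2 × (1 − 0.6)) = 0.894. Standard error = 0.894 × √(2/18) = 0.298. Detectable effect = (1.960 + 0.842) × 0.298 = 0.835, which matches 0.84.

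**2. Power is not the main issue.** With overall attrition held at 40%, splitting it 50/30 between the arms gives power 0.793 at 0.84, and 60/20 gives 0.757, against 0.804 when equal.

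**3. Path A: those withdrawn from SHUTi benefit less.** Take three visits with all correlations 0.6, withdrawal after the mid-point, and mid-point ISI kept. Let p be the share withdrawn, k the share of benefit they keep, d the final effect in those who stay and m their mid-point effect. The weight that the model gives the mid-point value is (0.6 − 0.36)/(1 − 0.36) = 0.375. Then

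bias = p × (1 − k) × (d − 0.375 × m).

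With d = 0.84 and m from 0.42 to 0.84, the last bracket runs from 0.6825 down to 0.525. The true effect in all randomised is 0.84 × (1 − p(1 − k)).

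| Withdrawn (of 30) | Benefit kept | True effect | Overstatement, SD | Ratio |
|---|---|---|---|---|
| 10% (3) | half | 0.798 | 0.026-0.034 | 1.03-1.04 |
| 20% (6) | half | 0.756 | 0.053-0.068 | 1.07-1.09 |
| 10% (3) | none | 0.756 | 0.053-0.068 | 1.07-1.09 |
| 20% (6) | none | 0.672 | 0.105-0.137 | 1.16-1.20 |

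Against the standard error: 0.026/0.298 = 0.09 and 0.137/0.298 = 0.46. A simulation with 1,000,000 per arm agrees: in the last row it gives 0.808 (m half of d) and 0.778 (m equal to d) against 0.672. At d = 0.2, the low end of the ISI range in Section 3, the same cases give 0.01-0.03 SD. For sleep efficiency at Section 3's d = 0.68, assuming the same correlation, they give 0.02-0.11 SD.

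**4. Path B: those withdrawn are prognostically worse, with no treatment effect.** Let a share m of the SHUTi arm be lost, with mean change g SD worse than those kept. Control loss is equal in size but uninformative, and the model does not recover the gap. Bias = m × g = 0.2 × 0.5 = 0.10 SD. With 30 × 0.8 = 24 per arm, the standard error is 0.894 × √(2/24) = 0.258 and 0.10/0.258 = 0.387. Type I error = 1 − Φ(1.960 − 0.387) + Φ(−1.960 − 0.387) ≈ 0.067. At the same 20% loss, gaps of 0.25 and 1.0 SD give bias 0.05 and 0.20 SD, and type I error 0.054 and 0.121. To the extent that mid-point ISI already shows the gap, the model recovers part of it and these figures shrink.

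**5. Path C: informative loss mainly among controls.** If readmission removes 20% of controls with the same 0.5 SD gap and SHUTi loss is uninformative, the sign reverses and the effect is understated by 0.10 SD.

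**The case against.** The best defence is that the compliance reason is narrow. It speaks of being *unable*, which echoes the entry criterion in Section 2.5.1 on capacity to meet study requirements, such as Internet access. Section 2.4 measures partial adherence, and the dose analysis in Section 3 presupposes that people with few cores reach an outcome assessment. On that reading few people are withdrawn, and the 10-20% above has no support in the documents. This largely stands. A reader might infer that Section 9 will strip poor adherers from the SHUTi arm, and the documents do not establish that. What remains is that Section 9 sets no threshold, names only SHUTi tasks, and must be reconciled with Sections 2.4 and 3.

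Other points also stand. Controls can be withdrawn under both reasons. The mixed model keeps earlier data. "The ISI is collected within the SHUTi intervention program at the beginning of each core" as well as on paper, although Section 3 does not say whether those values enter the model. Analysis by assigned arm is already implied by the use of every available observation and by the intent-to-treat paper that Section 3 cites. The size is modest for a pilot trial that plans for 24 of 60 to be lost (40%), much of which may be ordinary dropout. People who cannot comply may also not complete later assessments, and measurements on readmitted people may reflect an inpatient setting.

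None of this supplies a provision for assessment after withdrawal. The 40% allowance protects the sample size, not against bias.

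**Conclusion.** The gap is real: two of the listed reasons end study participation, and nothing in the documents keeps outcome assessment going. The loss that results may be informative and may differ by arm, so the MAR condition behind the claim of unbiasedness may fail.

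Two stronger inferences should be resisted. One is that the rule necessarily flatters SHUTi: that follows on Path A, but loss concentrated among controls (Path C) reverses it. The other is that there is no harm if SHUTi does nothing: Path A does give zero there, but Path B does not.

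On size, the illustrations are 0.03-0.14 SD of overstatement at d = 0.84 with 10-20% of SHUTi withdrawn, and 0.10 SD with type I error about 0.067 under no effect with 20% lost and a 0.5 SD gap. All rest on assumed withdrawal shares and gaps. The actual size cannot be derived from the documents. This is worth correcting because the remedy is cheap, but it does not invalidate the design.

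**What to change.** In Section 9, separate stopping the programme from leaving the study, leaving the reasons for stopping the programme as they are. Unless consent is withdrawn, and where feasible and safe, continue the scheduled ISI and drinking assessments by the phone route already in Sections 2.2 and 10, and actigraphy by the mail route already in Section 2.4. Record whether the participant was an inpatient at each such assessment. Reconcile the compliance wording with the treatment of partial adherence in Sections 2.4 and 3.

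In Section 3, state as a clarification that all randomised participants are analysed by assigned arm, including data collected after the programme was stopped.

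The cost is a few sentences, plus calls and watch mailings for perhaps 3 to 6 people if 10-20% of 30 SHUTi participants stop, and for any controls who do. Recovery will be incomplete, ordinary dropout is untouched, and the estimated effect may be smaller. Partial success still helps: in the 20%, no-benefit case, reaching a random half of those withdrawn cuts the bias from 0.11-0.14 to 0.04-0.06 SD (simulated 0.730 and 0.716 against 0.672). Those reached may not be a random half, so this is a favourable case.

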10.1 Data sharing plan

Data may be shared with collaborating laboratories at NIH or outside of NIH and/or submitted to NIH-designated repositories and databases if consent for sharing was obtained (if applicable: or under waiver of informed consent as described below). Repositories receiving data from this protocol may be open-access or restricted access. Samples and data will be stripped of identifiers and may be coded ("de-identified") or unlinked from an identifying code ("anonymized"). When coded data is shared, the key to the code will not be provided to collaborators, but will remain at NIH. Data and samples may be shared with investigators and institutions with an FWA or operating under the Declaration of Helsinki (DoH) and reported at the time of continuing review. Sharing with investigators without an FWA or not operating under the DoH will be submitted for prospective IRB approval. Submissions to NIH-sponsored or supported databases and repositories will be reported at the time of Continuing Review. Submission to non-NIH sponsored or supported databases and repositories will be submitted for prospective IRB

Protocol Number: 18-CC-0079

approval. Required approvals from the collaborating institution will be obtained and materials will be shipped in accordance with NIH and federal regulations.

